3.19g Willing to provide blood samples at baseline for correlative research purposes and tissue for central pathology review (see Sections 6.2, 14.0, and 17.0).

3.19h <25% bone marrow involvement of cellular marrow with lymphoma as determined by bilateral bone marrow aspirate and biopsy. NOTE: The percent involvement should be estimated by the hematopathologist using all of the biopsy material.

3.19i Has insurance coverage or is willing to pay for protocol therapy (rituximab x 4 or Zevalin x 1)

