7.0 Protocol Treatment

7.1 Treatment Schedule – Arm A: Rituximab

Agent	Dose	Route	Day	Cycle Length
Rituximab ¹	375 mg/m ² /day	IV	1, 8, 15, 22	3 months

1. Substitution of a rituximab biosimilar covered by patients' insurance plan is acceptable for Arm A.

The following pre-medications are suggested prior to rituximab: acetaminophen 650-1000 mg PO 30 minutes prior to rituximab and every 4 hours as needed for infusion related reactions, diphenhydramine 50 mg PO 30 minutes prior to rituximab, diphenhydramine 25 mg IV every 4 hours as needed for infusion related reactions, meperidine 25 mg IV push as needed for rigors, may repeat x 1 dose if first dose is ineffective

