7.2 Treatment Schedule – Arm B: Zevalin

Agent	Dose	Route	Day	Cycle Length
Rituximab ¹	250 mg/m ² /day	IV	1, 8	3 months
Zevalin	0.3 mCi/kg or 0.4 mCi/kg**	IV	8*	

- * Administer within 4 hours of completion of rituximab infusion.
- ** Maximum dose = 32 mCi. Dose at 0.4 mCi/kg for patients with platelet counts greater than or equal to 150,000/mm³ and at 0.3 mCi/kg for patients with platelet counts 100,000 to 149,000/mm³
- 1. Substitution of a rituximab biosimilar covered by patients' insurance plan is not allowed for Arm B.

The following pre-medications are suggested prior to rituximab: acetaminophen 650-1000 mg PO 30 minutes prior to rituximab and every 4 hours as needed for infusion related reactions (maximum of 4000 mg in 24 hours), diphenhydramine 50 mg PO 30 minutes prior to rituximab, diphenhydramine 25 mg IV every 4 hours as needed for infusion related reactions, meperidine 25 mg IV push as needed for rigors, may repeat x 1 dose if first dose is ineffective.

- 7.3 For this protocol, patients randomized to Zevalin can be treated either at the enrolling site or referred to Mayo Clinic Rochester, Arizona, or Florida for the Day 1, 8 rituximab and Zevalin on Day 8. The enrolling site is also permitted to provide Day 1 rituximab if this is prearranged and coordinated with the Zevalin site. This can be arranged by calling the study [REDACTED] after the patient has been registered.

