13.0 Treatment/Follow-up Decision at Evaluation of Patient

13.1 Patients will be evaluated per the test schedule during cycle 1 of treatment.

13.2 After treatment, patients will be observed at 3, 6, 9, 12, 18, 24, 30, 36, 48, and 60 months from day 1 of treatment.

13.3 Criteria for removing patients from treatment and initiating observation.

13.3.1 Requested withdrawal or patient non-compliance.

13.4 Patients who have progressive or relapsed disease, receive subsequent treatment for lymphoma, refuse further observation, or fail to return for evaluation during observation will go to event monitoring.

13.5 At 5 years from day 1 of treatment, all patients still on observation will go to event monitoring every 12 months until 10 years from time of registration per Section 18.0.

13.6 A patient is deemed *ineligible* if after registration, it is determined that at the time of registration, the patient did not satisfy each and every eligibility criteria for study entry.

The patient may continue protocol treatment at the discretion of the physician as long as there are no safety concerns, and the patient was properly registered. The patient will continue treatment (if no safety concerns), observation, and event monitoring as specified for all patients (or will be taken off study, if applicable).

- If the patient received treatment, the patient will continue treatment (if no safety concerns), observation, and event monitoring as specified for all patients.
- If the patient never received treatment, On-study material and the End of Active Treatment/Cancel Notification Form must be submitted. No further data submission is necessary.

13.7 A patient is deemed a *major violation*, if protocol requirements regarding treatment in cycle 1 of the initial therapy are severely violated that evaluability for primary end point is questionable. The patient may continue protocol treatment at the discretion of the physician as long as there are no safety concerns, and the patient was properly registered. The patient will continue treatment (if no safety concerns), observation, and event monitoring as specified for all patients.

13.8 A patient is deemed a *cancel* if he/she is removed from the study for any reason before any study treatment is given. On-study material and the End of Active Treatment/Cancel Notification Form must be submitted. No further data submission is necessary.

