16.0 Statistical Considerations and Methodology

16.1 Overview: This is a randomized phase III study designed to compare the complete response rate at 6 months between Rituximab (Arm A) and Zevalin (Arm B) for treatment of asymptomatic follicular lymphoma.

16.11 Primary Endpoint: The primary endpoint of this study is the complete response rate at the 6-month disease assessment which will be compared between the two arms. A patient is considered to be a complete responder if the objective status at the 6-month disease assessment is a complete response. Any patient not meeting the definition of a complete response will be considered as a non-responder for the primary endpoint. A modified intent-to-treat approach will be employed for the primary analysis such that all randomized subjects meeting the eligibility criteria who do not cancel participation prior to treatment initiation and did not experience a major treatment violation (during the first cycle of treatment) will be included in the primary analysis. Sensitivity analysis will be conducted including all patients who did not cancel participation prior to

treatment initiation. The percentage of patients in each response category (e.g., CR, PR, STAB, Relapse/PD) will also be tabulated by arm.

16.2 Statistical Considerations:

16.21 Statistical Design:

Previous studies of treatment with four doses of single agent Rituximab in this patient population have shown CR rates of 6-33% (9 and 10). In addition, preliminary results of an additional study, the RESORT ECOG trial, show a CR rate of 15% in this same population (11). This study is designed to detect an improvement in complete response rate from 20% with Rituximab (Arm A) to 50% with Zevalin (Arm B). The proportion of patients who have a CR at 6 months will be evaluated and compared between the two treatment regimens using a two-sided $\alpha=0.05$ continuity corrected Cochran–Mantel–Haenszel (CMH) test with stratification factors as defined in Section 5.0.

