19.0 Budget

- 19.1 Costs charged to patient: rituximab and Zevalin are standard of care and will be commercial
- 19.2 Tests to be research funded: Lymphoma SPORE will cover the research translational costs and kits and mailing. This will involve the clinical trials core B and the Biospecimens Core.
- 19.3 Other budget concerns: Protocol administration, study coordinator time, data management, and statistical analysis efforts will be funded by Acrotech Biopharma.

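### Criterion 3.19i does not confirm before randomisation that a patient has access to Arm B's rituximab, so pre-treatment loss can depend on the assigned arm and no planned CR analysis would show it

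*Combined protocol and SAP*

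**What the plan says.** **Who pays.** Section 19.1: "Costs charged to patient: rituximab and Zevalin are standard of care and will be commercial". Criterion 3.19i, checked before registration, requires that the patient "Has insurance coverage or is willing to pay for protocol therapy (rituximab x 4 or Zevalin x 1").

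**What each arm contains.** Arm A is four rituximab infusions (7.1). Arm B is rituximab on days 1 and 8, with Zevalin on day 8 (7.2): "Administer within 4 hours of completion of rituximab infusion".

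**Biosimilars.** Footnote 1 in 7.1: "Substitution of a rituximab biosimilar covered by patients' insurance plan is acceptable for Arm A". Footnote 1 in 7.2: "Substitution of a rituximab biosimilar covered by patients' insurance plan is not allowed for Arm B".

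**What happens to patients who do not start.** Under 13.8 a patient is a cancel "if he/she is removed from the study for any reason before any study treatment is given". Only on-study material and the cancellation form are then submitted.

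**Who is analysed.** Section 16.11 defines the primary set as "all randomized subjects meeting the eligibility criteria who do not cancel participation prior to treatment initiation and did not experience a major treatment violation" in cycle 1. The one alternative set also drops cancels: "Sensitivity analysis will be conducted including all patients who did not cancel participation prior to" treatment initiation.

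**The concern.** Randomisation protects the CR comparison only if the patients who enter the analysis do so independently of the arm they drew. Here the product rule differs by arm, the drug is charged to the patient, and the entry criterion does not mention one component of Arm B. A coverage problem can therefore surface only once the arm is known. Section 6.6 then allows 21 days from registration to start treatment.

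This is out of step with the rest of the eligibility section, which screens every patient for the ability to receive Arm B: the radioimmunotherapy criteria (3.18), willingness to travel for Zevalin (3.19e) and marrow involvement (3.19h).

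The issue is detectability as much as occurrence. If such losses happened, they would be absent from both planned CR analyses, no response data would exist for them, and the plan does not call for a comparison of cancels by arm.

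**Working it through.** **1. The gap under both readings of 3.19i.** The bracketed *or* can be read strictly (cover for whichever arm is drawn) or literally (cover for either regimen is enough). Take a patient whose plan covers Zevalin, but rituximab only as a biosimilar.

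| Step | Result |
|---|---|
| 3.19i, strict reading | Met: rituximab x 4 is covered (as a biosimilar, which 7.1 accepts) and so is Zevalin x 1 |
| 3.19i, literal reading | Met |
| Drawn to Arm A | Treated under 7.1, footnote 1 |
| Drawn to Arm B | Rituximab on days 1 and 8 may be uncovered (7.2, footnote 1); can start only by self-paying |
| If treatment does not start | Cancel (13.8); out of the primary and sensitivity analyses (16.11) |
| If the biosimilar is given anyway | Departs from 7.2; if judged a major violation (13.7), out of the primary analysis but kept in the sensitivity analysis |

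The gap does not depend on how *or* is read.

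**2. The plan's sample size.** Inputs from 16.21: CR 20% against 50%, two-sided alpha 0.05, 90% power, 1:1 allocation. The continuity-corrected two-proportion formula gives 58 per arm, matching the plan; without the correction it gives 52. Exact power of the continuity-corrected chi-square test (unstratified) at 58 against 58 is 90.6%. The allowance is 128 − 116 = 12 patients, 12/128 = 9.4%, for all causes and both arms.

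**3. Effect on power.** The documents give no coverage data, so the Arm B loss f is an assumption, from 5% to 20%.

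- *No other losses, 64 randomised per arm.* At f = 15%, 64 × 0.15 = 9.6, leaving about 54 in Arm B against 64 in Arm A. The total is 118, above the 116 required. Exact power is 91.5%.
- *Allowance already used, 58 per arm before this loss.* At f = 5%, 10%, 15% and 20%, Arm B keeps 55, 52, 49 and 46. Exact power is 90.5%, 89.4%, 87.7% and 86.2%.

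**4. Effect on the estimate.** If the lost patients would have had CR rate q and the whole of Arm B 50%, the retained Arm B rate is (0.50 − f × q)/(1 − f). The values of q are assumptions.

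- q = 30%: f = 5% gives 0.485/0.95 = 51.1%; f = 10% gives 0.470/0.90 = 52.2%; f = 20% gives 0.440/0.80 = 55.0%.
- q = 50%: no change at any f.
- q = 70%, f = 10%: 0.430/0.90 = 47.8%.

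The shift can go either way, and is zero if insurance type is unrelated to response.

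**5. Counting cancels as non-responders.** With 64 per arm and losses only in Arm B, the Arm B rate is 0.50 × (1 − f): 50%, 47.5%, 45% and 40% at f = 0, 5%, 10% and 20%. Power by the uncorrected formula is 95.4%, 91.8%, 86.4% and 69.9%.

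**The case against.** The strongest reply is that 3.19i is adequate as it stands. It is written before the arm is known, so the bracket can be read as listing the two possible assignments, with cover needed for whichever is drawn. Section 7.2 titles the whole Arm B regimen as Zevalin, so Zevalin x 1 may be shorthand that includes the two rituximab infusions. Patients may also pay for themselves, and biosimilar-only cover may be rare.

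Much of this stands. The strict reading is natural, and nothing in the documents excludes a frequency near zero. But even as shorthand, the criterion does not tell the registering site that cover for Arm B's rituximab must be for something other than the biosimilar that suffices in Arm A.

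Three stronger inferences are tempting and should not be drawn.

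- *Cover for either regimen alone is enough, so Arm B is depleted.* This is only one reading of *or*. Taken literally it also admits patients covered for Zevalin but not for rituximab x 4, who would be lost from Arm A. The loss is then not one-sided. Only the biosimilar route is.
- *The trial becomes underpowered.* An Arm B of 54 looks short of 58 only if the 64 in Arm A are ignored (step 3).
- *The CR comparison is biased.* That needs insurance type to be related to six-month CR, on which the documents say nothing. With an assumed 30% CR in lost patients, the Arm B rate moves 1.1 to 2.2 points at 5% to 10% loss, against a designed difference of 30 points.

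Nor do the two footnotes contradict each other: they set different rules for different arms.

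**Conclusion.** The point holds as a gap in the entry criterion combined with the handling of cancels. As written, 3.19i does not ensure that every randomised patient can receive either arm as specified. Arm-dependent cancellation is therefore possible, and no planned CR analysis would reveal it.

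Its size is unknown. The documents give neither the share of patients with biosimilar-only cover nor any link between cover and response. Under an assumed 5% to 15% loss confined to Arm B, 64 × 0.05 = 3.2 to 64 × 0.15 = 9.6 patients would be affected. The sample size is sound, and power changes little over that range. A reader might conclude that prevention at entry is the only remedy. It is not: cancels could in principle be followed to month 6, or counted in an all-randomised analysis. Prevention is simply the cheapest step. The change is worth making, but this is not a fatal defect.

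**What to change.** 1. **Reword 3.19i**, for example: *Before registration, insurance coverage of, or willingness to pay for, both regimens as specified in Sections 7.1 and 7.2 has been confirmed, including the rituximab given in Arm B.* The registration application already verifies eligibility (6.4), so no separate check is needed.
2. **Report cancels and their reasons by arm** with the primary result. This also helps for patients already enrolled.
3. **Add a sensitivity analysis of all randomised patients**, with cancels counted as non-responders. It cannot recover missing responses. If losses fall in Arm B it is conservative against Zevalin and loses power (step 5), so it belongs beside the primary analysis, not in its place.

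The cost is one eligibility sentence, one table and one extra analysis. The downside is small: some patients are screened out before randomisation instead of being lost after it. Which product either arm uses is left as the protocol has it.

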3.2 Exclusion Criteria

3.21 Any of the following because this study involves an agent whose genotoxic, mutagenic and teratogenic effects on the developing fetus and newborn are unknown:

- Pregnant women
- Nursing women
- Men or women of childbearing potential who are unwilling to employ adequate contraception for at least three months after completing study treatment.

3.22 Co-morbid systemic illnesses or other severe concurrent disease which, in the judgment of the investigator, would make the patient inappropriate for entry into

this study or interfere significantly with the proper assessment of safety and toxicity of the prescribed regimens.

- 3.23 Patients known to be HIV positive and currently receiving antiretroviral therapy.
- 3.24 Uncontrolled intercurrent illness including, but not limited to, ongoing or active infection, symptomatic congestive heart failure, unstable angina pectoris, uncontrolled cardiac arrhythmia, or psychiatric illness/social situations that would limit compliance with study requirements.
- 3.25 Receiving any other investigational agent that would be considered as a treatment for the lymphoma.
- 3.26 Active other malignancy requiring treatment that would interfere with the assessments of response of the lymphoma to protocol treatment and would interfere with follow-up assessments through year 5.
- 3.27 Presence of CNS lymphoma.
- 3.28 Known to have lymphoma related to HIV or AIDS. NOTE: These patients are excluded because it is unknown what effects prolonged B-cell depletion will have on these patient's immune system.
- 3.29a Abnormal renal function (serum creatinine $>2 \times$ ULN).
- 3.29b Received prior external beam radiation therapy for another reason to $>25\%$ of active bone marrow (see form in Appendix IV).
- 3.29c Serious non-malignant disease such as active infection or other condition which in the opinion of the investigator would compromise other protocol objectives.
- 3.29d Major surgery other than diagnostic surgery ≤ 4 weeks prior to registration.
- 3.29e Any evidence of myelodysplastic syndrome or marrow chromosomal changes suggesting myelodysplasia (-7, -5 etc).
- 3.29f Corticosteroid therapy at the time the patient enters the protocol. NOTE: Patients using prednisone or its equivalent for adrenal failure or using ≤ 10 mg of prednisone/day for other benign causes are accepted.
- 3.29g Follicular grades IIIA or IIIB are not eligible.
- 3.29h Marrow cellularity $\leq 15\%$ (as determined on all bone marrow samples).
- 3.29i Seropositive for or active viral infection with hepatitis B virus (HBV):
 - HBsAg positive

- HBsAg negative, anti-HBs positive and/or anti-HBc positive and detectable viral DNA

Notes:

- Subjects who are HBsAg negative, anti-HBs positive, and/or anti-HBc positive, but viral DNA negative are eligible.
- Subjects who are seropositive because of HBV vaccination are eligible (HBV surface antibody positive, HBV core antibody negative, and HBV surface antigen negative).

3.29j Active infection with hepatitis C virus (HCV).

4.0 Test Schedule

Tests and procedures	Baseline (Prior to Registration)	Active Monitoring*			
		Cycle 1		Observation	
	≤28 days prior to reg.	Week 5,6, 7 post Zevalin for Arm B pts only	Month 3 post Day 1 of treatment ^{11,12}	Month 6 post Day 1 of treatment ^{11,12}	Months 9, 12, 18, 24, 30, 36, 48, 60 post Day 1 of treatment ^{11,12}
History and exam, weight, PS	X			X	
Height	X				
Tissue confirmation of FL grade I or II from routine diagnostic tissue ≤365 days prior to registration ⁸	X				
Adverse event assessment	X		X	X	
Hematology: WBC, ANC, ALC, AMC, Hgb, PLT	X	X ⁹	X	X	X
Lactate dehydrogenase (LDH) - include ULN	X			X	X
Chemistry: Creatinine, Glucose, SGOT (AST), Alk phos, Ca, T. Bili, uric acid	X			X	
Beta-2 microglobulin (B2M)	X			X	
Direct bilirubin ³	X				X
Serum pregnancy test ¹	X				
Bone marrow biopsy – unilateral or bilateral	X ⁵			X ⁶	
Tumor Measurement/Evaluation of indicator lesion (CT, MRI, etc.) CT Scan chest, abdomen and pelvis or PET/CT; measurements should be by CT or the CT portion of a PET/CT. May use MRI in situations that identify lesion more clearly than CT ²	X			X	X (months 12, 24, 36, 48, 60)
Research tissue ^R	X ⁴				
Research bloods ^{7,R}	X			X	
Hepatitis B and C screen ¹⁰	X				
Quantitative serum immunoglobulins: IgG, IgA, IgM	X ⁵				
QOL (FACT-Lym)	X ¹³		X ¹³	X ¹³	X ¹³

1. For women of childbearing potential only. Must be done ≤7 days prior to registration.
2. Use the same method throughout the study. See Section 11.0 for response criteria.
3. To be done only if the total bilirubin is abnormal.

4. Patients will be requested to submit paraffin embedded tumor for research purposes. This is optional and the patient can participate in the study without providing this sample. Patients at Mayo Clinic will be requested to provide an optional fresh research biopsy.
5. Bone marrow and immunoglobulins acceptable within 180 days prior to registration.
6. Repeat bone marrow only in patients with an initial positive bone marrow
7. Research bloods at baseline (visit 1/screening) and end of six months (visit 2/End of Cycle 2) only. The baseline samples can be collected after the patient consents but prior to starting treatment.
8. Patient can be registered with local pathology review; central review will be done on all cases (see Section 17.0).
9. CBCs should be drawn weekly or until ANC \geq 1000 and platelets \geq 50,000 at physician discretion.
10. Hepatitis B surface antigen (HbsAg) and antibody to Hepatitis B core (anti-HBc); Hepatitis C antibody. All patients must be screened prior to registration. Those patients who have evidence of chronic or acute infection with either hepatitis B or C may not be treated on this protocol.
11. \pm 1 week.
12. Data at the Month 3 visit is entered as Cycle 1. Data at the Month 6, 9, and 12 visits are entered as Cycle 2, 3, and 4, respectively. Data at the Month 18, 24, 30, and 36 visits are entered as Cycle 5, 6, 7, and 8, respectively. Data at the Month 48 and 60 visits are entered as Cycle 9 and 10, respectively.
13. Patient questionnaire booklet must be used; copies are not acceptable for this submission. Booklet for baseline visit should be completed prior to starting treatment. Patient should be given a booklet to complete in clinic prior to review of the patient's treatment response and discussions of patient's general health since last treatment evaluation.

R. Research funded (see Section 19.0).

5.0 Stratification Factors

- 5.1 Diagnosis: < 3 months vs. 3-12 months.
- 5.2 Beta-2 Microglobulin (using institutional values): normal vs. abnormal.
- 5.3 Lactate Dehydrogenase (using institutional values): normal vs. abnormal.

6.0 Registration Procedures

- 6.1 To register a patient, access the Lymphoma SPORE web page and enter the remote registration/randomization application. The registration/randomization application is available 24 hours a day, 7 days a week. Back up is available between 8 a.m. and 4:30 p.m. Central Time (Monday through Friday) by phone at [REDACTED]
[REDACTED]

The instructions for registration/randomization application are available on the Lymphoma SPORE secured web page and detail the process for completing and confirming patient registration. Prior to initiation of protocol treatment, this process must be completed in its entirety and a Lymphoma SPORE subject ID number must be available as noted in the instructions. It is the responsibility of the individual and institution registering the patient to confirm that the process has been successfully completed prior to release of the study agent. Patient registration via the registration/randomization application can be confirmed in any of the following ways:

- Contact the Lymphoma SPORE Registration Office [REDACTED] If the patient was fully registered, the Lymphoma SPORE Registration Office staff can access the information from the centralized database and confirm the registration.
- In the registration/randomization application, select the *Show Subject* button to verify that the patient registration data is retrievable.
- Enter the registration/randomization application and, using the Lymphoma SPORE subject ID, confirm the patient appears in the registration/randomization application.

